# 7.3. RETESTS, UNSCHEDULED VISITS AND EARLY TERMINATION DATA

For by-visit analyses and summaries of efficacy and safety, data (including scheduled, retests, unscheduled, and early termination) will be assigned to visits after the application of the windowing conventions described in Section 7.4. All measurements will be considered in summaries of abnormalities or worst-case values post-baseline.

In the case of a retest (same visit number assigned), the measurement nearest to the visit date will be used for by-visit summaries. In the case of several measurements equally close to the visit date, the earliest non-missing measurement will be taken. If multiple assessments are available on the same day, then the average of the assessment will be used in the analysis except for laboratory and ECG data, where the assessment at the earliest time of the same day will be used. If both central and local assessments of the same laboratory test are available on the same day, the central assessment will take precedence over the local assessment. Listings will include scheduled, unscheduled, retest and early discontinuation data.

#### 7.4. WINDOWING CONVENTIONS

All scheduled study visits are defined relative to Study Day 1, the date of randomization and first dose of study treatment. Scheduled visit windows are defined in Appendix 1 of the protocol. A windowing convention will be used to determine the analysis visit value for a given measurement and will be applicable for all by-visit summaries and analyses for efficacy and safety data. The early discontinuation visits and unscheduled visits will be eligible for allocation to an analysis visit. The 2-week follow-up visit will be summarized separately.

displays the specific visit windows used for the FAS, SAF and Per Protocol Set populations for efficacy and safety analysis. See

Additional Visit Windows for additional visit windows.

Windowing will be applied to the data prior to any missing data calculations. If one or more results for a variable are assigned to the same analysis visit, the result with the date closest to the protocol scheduled day will be used in the analysis. If two measurements in the same analysis visit window are equally close to the protocol scheduled study day, the earliest measurement will be used in the analysis. For ePRO measurements (PROMIS, EQ-5D, etc.), the stamp date in the device will be used to calculate the study day, and Day 1 will include those ePROs collected on Randomization Date or the date after randomization day (Day 1

and Day 2).

## 7.5. STATISTICAL TESTS

The default significance level will be 5%; confidence intervals (CIs) will be 95% and all tests will be two-sided, unless otherwise specified in the description of the analyses.

## 7.6. COMMON CALCULATIONS

For quantitative measurements:

• Change from baseline = (Test Value at Visit X – Baseline Value)

- Percent change from baseline = ((Test Value at Visit X Baseline Value) / Baseline Value) x 100
- Proportion at Visit X = (Number of subjects satisfying criteria at Visit X / Total number of subjects at Visit X)
- Proportion achieving an improvement from Visit X to Visit Y = (Number of subjects achieving an improvement from Visit X to Visit Y / Total number of subjects with non-missing data for that parameter at both Visit X and Visit Y)

#### 7.7. GENERAL STUDY INFORMATION

All analyses, except for PK, will be conducted using SAS® (version 9.4 or later, SAS Institute Inc., Cary, NC).

For PK, non-compartmental parameter calculations will be performed using Phoenix® WinNonlin® 8.0 or higher (Certara, L.P., Princeton, New Jersey). Graphics may be prepared using the same versions of SAS®. A general table with summary of study information will be generated, including date first subject signed ICF, last subject last visit date, database lock date and versions of the MedDRA, World Health Organization Drug Dictionary Global (Enhanced w/WHO Herbal Dictionary) (WHODD), and software used for analyses (SAS, WinNonlin) etc.

#### 8. SAMPLE SIZE JUSTIFICATION

It is assumed that change in AAPS from Main Study baseline to Week 12 will be normally distributed with a standard deviation (SD) of 1.9. Assuming a 1:1:1:1 randomization, 240 subjects (60 per treatment group) is sufficient to achieve at least 80% power to detect a treatment effect of 1.0 between each of the olorinab treatment groups and placebo by a 2-sample t-test using a 2-sided significance level of 0.05. Note, under the same assumptions there is at least 95% power to detect a treatment effect of 1.0 between the pooled olorinab treatment group (180 subjects) and placebo (60 subjects).

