## 6.4. Subject Discontinuation of Study

Subjects will be free to withdraw from the study at any time should they wish to do so. Any subject may be discontinued early from the study for any of the following reasons:

- AE
- Withdrawal by subject
- Investigator decision
- Lost to follow-up (Section 6.5)
- Study termination by Sponsor
- Death
- Protocol deviation
- Pregnancy
- Other

Subjects who withdraw from the study will be encouraged to return to the site to complete an Early Termination visit Subjects who withdraw from the study will not be replaced by additional subjects.

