#### 18.1.3. PRIMARY ANALYSIS OF PRIMARY EFFICACY VARIABLE

The primary efficacy analysis will be performed using the FAS population. The primary efficacy endpoint will be analyzed using a MMRM analysis with treatment group (placebo, olorinab 10 mg, olorinab 25 mg, olorinab 50 mg), stratification factors (sex and IBS subtype), week, and treatment-by-week interaction as factors and baseline AAPS as a covariate. Week will include each week from Week 1 to Week 12 based on eDiary data beginning from Day 1 (Randomization). In addition, two additional MMRMs will be completed with the following treatment groupings: 1) placebo, olorinab 10 mg, and olorinab 25 and 50 mg pooled and 2) placebo and pooled olorinab.

The primary objective of this study is to test the hypothesis that the change in AAPS from baseline to Week 12 is the same across treatment group (placebo, olorinab 10 mg, 25 mg, and 50 mg). The alternative hypothesis is that the change in AAPS from baseline to Week 12 differs between placebo and one of the olorinab treatments (10 mg, 25 mg, or 50 mg) or olorinab 25 mg/50 mg pooled.

Four hypothesis tests for the primary endpoint using the primary analysis methodology

described above are specified below.

- MMRM model with treatment groups (placebo, 10 mg, 25 mg, and 50 mg), and with
   3 pre-specified comparisons of placebo vs. the individual treatment groups of olorinab (10 mg, 25 mg, and 50 mg)
- MMRM with treatment "groups" placebo, 10 mg, and pooled olorinab [25 mg + 50 mg], and with 1 pre-specified comparison of placebo vs. the pooled olorinab group [25 mg + 50 mg]

No multiplicity control is planned for this Phase 2 study. If any of the four pre-specified hypothesis test analyses demonstrates statistical significance at the 0.05 (2-sided) significance level at Week 12, then the study successfully demonstrated that the primary endpoint was met.

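### The stated power for all olorinab doses pooled versus placebo is about 94%, just short of the 95% lower bound given

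*SAP*

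**What the plan says.** SAP section 8 takes the change in average abdominal pain score (AAPS) from baseline to Week 12 to be "normally distributed with a standard deviation (SD) of 1.9". It sets the design as "Assuming a 1:1:1:1 randomization, 240 subjects (60 per treatment group") and claims "at least 80% power to detect a treatment effect of 1.0 between each of the olorinab treatment groups and placebo", tested "by a 2-sample t-test using a 2-sided significance level of 0.05". A note then adds that, with those assumptions kept, "there is at least 95% power to detect a treatment effect of 1.0 between the pooled olorinab treatment group", of 180, and a placebo group of 60. Protocol section 8.1 and the sample size paragraph of the synopsis make the same two claims.

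SAP 18.1.3 lists four hypothesis tests for the primary endpoint. Three compare a single dose with placebo. The fourth is "1 pre-specified comparison of placebo vs. the pooled olorinab group", where the pooled group is 25 mg plus 50 mg. The primary endpoint counts as met if any one of the four is significant at the two-sided 0.05 level. All three doses pooled versus placebo is also analysed, but it is not one of the four.

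The sample size sections give no loss rate. Protocol 6.4 says "Subjects who withdraw from the study will not be replaced by additional subjects".

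**The concern.** A power given as a lower bound, with every input supplied, can be checked exactly. If it falls short, the protocol and SAP carry a wrong figure that may be copied into the study report. There is also a mismatch of subject. The only pooled power given belongs to a comparison outside the success rule, while the pooled test inside the rule has none. What is at stake is the accuracy of a stated design property, not the size of the trial.

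**Working it through.** **Inputs** (SAP section 8, repeated in Protocol 8.1): SD = 1.9; difference = 1.0; two-sample t-test; two-sided alpha = 0.05; 60 per arm. The 120 for 25 mg plus 50 mg is 2 × 60.

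**Formulas.** Standard error SE = 1.9 × √(1/n₁ + 1/n₂). Noncentrality λ = 1.0 / SE. Power by t-test = P(|T| > t₀.₉₇₅), with T noncentral t on n₁ + n₂ − 2 degrees of freedom and noncentrality λ. Power by normal approximation = Φ(λ − 1.960).

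| Comparison | SE | λ | df | t₀.₉₇₅ | Power (t) | Power (normal) | Plan states |
|---|---|---|---|---|---|---|---|
| One dose vs placebo, 60 v 60 | 0.3469 | 2.883 | 118 | 1.980 | 81.6% | 82.2% | at least 80% |
| All doses vs placebo, 180 v 60 | 0.2832 | 3.531 | 238 | 1.970 | 94.0% | 94.2% | at least 95% |
| 25+50 mg vs placebo, 120 v 60 | 0.3004 | 3.329 | 178 | 1.973 | 91.2% | 91.4% | nothing |

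The per-dose claim reproduces, so the method matches the plan's. The all-dose claim comes close, but 94.0% and 94.2% are both below the bound.

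**What would reach 95% for all doses pooled.** At 3:1 allocation, 63 per arm gives 94.99% and 64 per arm gives 95.3% by t-test. With the planned numbers, an SD of 1.85 gives 95.1%. A one-sided 0.05 test would give 97.0%, but the plan specifies two-sided.

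**The success rule as a whole.** With a true effect of 1.0 at every dose, SD 1.9 and 60 per arm, simulating the four t-type tests gives about a 96% chance that at least one is significant.

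**Loss of subjects (assumed; the plan gives no rate).** Removing the same fraction from every arm and counting leavers as contributing nothing:

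| Evaluable per arm | One dose | 25+50 mg pooled | All doses pooled |
|---|---|---|---|
| 60 (no loss) | 0.8157 | 0.9116 | 0.9402 |
| 57 (5%) | 0.7955 | 0.8972 | 0.9288 |
| 54 (10%) | 0.7734 | 0.8808 | 0.9153 |
| 51 (15%) | 0.7493 | 0.8620 | 0.8997 |

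**The case against.** The best defence is that the shortfall is one point, in a side note, in a Phase 2 study that declares its comparisons exploratory and does not control type I error. The sample size comes from the per-dose claim, which is right. All of this stands, and it is why the point is minor. It does not make the sentence true: the plan gives a lower bound, and both usual methods fall below it.

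A second defence is that the planned analysis is a mixed model for repeated measures (MMRM) adjusted for baseline AAPS, sex and IBS subtype, which may be more powerful than a t-test. If the covariates explained about 5% of the variance (an assumption; a correlation of about 0.23), the residual SD would be about 1.85 and the power about 95%. That is possible, but the sentence rests on the t-test assumptions and the plan quantifies no gain.

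Three stronger readings are tempting, and the documents do not support them:

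- A reader might infer that several pooled power claims are wrong. The plan makes only one. It claims nothing for 25 mg plus 50 mg, so 91.2% fills a gap and contradicts no figure. Confusing the two comparisons is unlikely, because the 95% is printed with its group sizes of 180 and 60.
- A reader might infer that the 25+50 mg test decides success, so that the chance of success is about 91%. It is one of four routes, any of which suffices, and the rule as a whole has about a 96% chance under the plan's effect at every dose.
- A reader might infer that withdrawals take the per-dose power below 80%. The loss rates tabulated above are assumed, and the calculation discards leavers entirely. SAP 18.1.2 has the MMRM use all available treatment-period data, so partial records still contribute. The table shows sensitivity and is not a forecast.

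**Conclusion.** One stated figure is slightly wrong. For all doses pooled versus placebo the power is 94.0% (94.2% by the normal approximation), about one point below the stated bound. This rests only on the plan's own SD, effect, test, alpha and group sizes, with all 60 subjects per arm evaluable at Week 12. The missing power for 25+50 mg versus placebo, about 91% on the same basis, is a secondary omission. Neither point affects the sample size, the analysis or the success rule. Severity: minor.

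**What to change.** In the protocol synopsis (sample size), Protocol section 8.1 and SAP section 8, replace the lower bound of 95% for 180 versus 60 with about 94%.

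Optionally, in the same places, add two statements. First, 25 mg plus 50 mg versus placebo (120 versus 60), the only pooled test among the four in SAP 18.1.3, has about 91% power. Second, all power figures assume 60 evaluable subjects per arm.

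The cost is wording in three places and slightly less favourable figures. No patients are added, and no analysis or decision rule changes.

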#### 9. STATISTICAL CONSIDERATIONS

# 9.1. ADJUSTMENTS FOR COVARIATES AND FACTORS TO BE INCLUDED IN ANALYSES

The following covariates and factors are used in the analyses. For details of their inclusion in the models, see the specific analysis section.

- Baseline AAPS value
- Treatment: (Placebo, Olorinab 10 mg, Olorinab 25 mg, Olorinab 50 mg) and, additionally for primary and secondary efficacy endpoints, (Placebo and Olorinab pooled; Placebo, Olorinab 10 mg, Olorinab 25 and 50 mg pooled)
- Stratification factors:
  - Sex: Male, Female
  - IBS subtype: IBS-C, IBS-D
- Week: Week 1 Week 14
- Scheduled Visit: Day 1, Week 2, Week 4, Week 8, Week 10, Week 12, Week 14
- Treatment-by-week interaction
- Treatment-by-visit interaction

#### 9.2. MULTICENTER STUDIES

This study will be conducted by multiple investigators at multiple investigational sites within the United States. Randomization to treatment arms is not stratified by center. Randomization to treatment arms is stratified by sex (male, female) and IBS subtype (IBS-C, IBS-D). Data from all sites will be pooled and statistical analyses will not be adjusted for investigational site or geographic region. Ad-hoc analyses may be conducted by site or by pooling sites.

#### 9.3. MISSING DATA

Missing safety data will generally not be imputed, with the exceptions of AE relationship to study treatment (as described in Section 19.1.3), partial or missing AE start dates, and Concomitant Medication (CM) start dates. Details about date imputations are described in Appendix 2. Partial Date Conventions. No other missing safety data will be imputed.

Missing efficacy data will be handled as described in Sections 18.1.2, 18.2.2, and 18.3.21 of this analysis plan. Sensitivity analyses will be conducted to assess the robustness of the

primary and secondary endpoint results, as described in Sections 18.1.4 and 18.2.4, respectively. Missing PK data will be handled as described in Section 20.2 of this analysis plan.

#### 9.4. MULTIPLE COMPARISONS/ MULTIPLICITY

No formal testing strategy or adjustments of the type I error will be employed for the primary, secondary or exploratory endpoints. Estimates and CIs for treatment groups and from pairwise comparisons will be used in an exploratory manner.

#### 9.5. EXAMINATION OF SUBGROUPS

The following subgroups will be assessed for the primary endpoint:

- Sex (Female, Male)
- IBS subtype (IBS-C, IBS-D)
- Stratification factor (Female IBS-C, Female IBS-D, Male IBS-C, Male IBS-D)
- Baseline AAPS (< Median, ≥ Median)
- Age ( $\leq$  Median,  $\geq$  Median)
- Race (Caucasian, Non-Caucasian)
- Ethnicity (Hispanic, Non-Hispanic)
- Baseline BMI (< Median, ≥ Median)
- Baseline Duration of IBS (< Median, > Median)
- Baseline IBS-SSS (<75 (remission),  $\geq 75$  and <175 (mild),  $\geq 175$  and <300 (moderate),  $\geq 300$  (severe))
- Baseline IBS-QoL (>40 (non-severe), ≤40 (severe))
- Baseline HADS anxiety scores ( $\geq 8$  or  $\leq 8$ )
- Baseline HADS depression scores ( $\geq 8 \text{ or } < 8$ )

Additional subgroups may be assessed, if deemed necessary. It should be noted that the study was not designed to detect treatment differences with statistical power within any of the above subgroups.

#### 10. OUTPUT PRESENTATIONS

Appendix 1. Programming Conventions for Outputs shows conventions for presentation of data in outputs. The templates provided with this SAP describe the presentations for this study and therefore the format and content of the summary tables, figures, and listings to be

provided for the clinical study report.

#### 11. DISPOSITION AND PROTOCOL DEVIATIONS

All subjects who provide informed consent will be accounted for in this study.

Subject disposition and withdrawals will be provided for the FAS. This summary will note subjects who complete the Week 12 visit as well as subjects who complete the Week 14 visit. An analysis set listing will also be provided. Inclusion and exclusion criteria will be presented for the screened set.

Protocol deviations will be displayed for the FAS. Deviations will be categorized as Critical/Major or Minor. Critical/major deviations will be summarized by treatment (placebo, olorinab 10 mg, olorinab 25 mg, olorinab 50 mg), olorinab 25 and 50 mg pooled, and olorinab pooled for the following categories as described in the Protocol Deviation and Classification Guidance document. All critical/major deviations will also be listed.

- Informed Consent Criteria
- Eligibility and Entry Criteria
- Concomitant Medication Criteria
- Laboratory Assessment Criteria
- Study Procedures Criteria
- SAE Criteria
- Randomization Criteria
- Visit Schedule Criteria
- Investigational Product Compliance
- Efficacy Criteria
- Administrative Criteria
- Source Document Criteria
- Regulatory or Ethics Approvals Criteria
- Other Criteria

A summary of protocol deviations related to COVID-19 will also be presented, as well as a listing of subjects with study conduct impacted by COVID-19.

#### 12. DEMOGRAPHICS AND BASELINE CHARACTERISTICS

Demographics and baseline characteristics data will be presented for the FAS and Safety Set.

The data will be summarized by treatment, olorinab 25 and 50 mg pooled, and olorinab 10, 25, and 50 mg pooled without statistical testing. The following demographic and baseline characteristics will be reported for this study:

- Age on consent (years)
- Sex at birth: Female and Male
- Child-bearing potential for women: Yes, No
- Race: American Indian or Alaska Native, Asian, Black or African American, Native Hawaiian or Other Pacific Islanders, Multiple, White, Not Reported
- Race group: White, Non-White, Not Reported
- Ethnicity: Hispanic or Latino, Non-Hispanic or Latino, Not Reported, Unknown
- Weight (kg)
- Height (cm)
- BMI  $(kg/m^2)$
- •
- •
- •
- Time since IBS diagnosis (years) calculated relative to date of randomization
- IBS subtype: IBS-C, IBS-D
- eDiary Compliance Rate (%)
- Baseline AAPS
- Baseline AAPS Category:  $(\le 7, >7)$
- •

## 12.1. DERIVATIONS

- BMI  $(kg/m^2)$  = weight (kg)/ height  $(m)^2$
- Time since IBS diagnosis (years) = (date of randomization date of IBS diagnosis + 1) / 365.25
  - o Partial dates are imputed to the earliest possible date
- Weight (kg) = Weight (lb) \* 0.4536
- Height (cm) = Height (in) \*2.54
- Height (m) = Height (in) \*0.0254 = Height (cm) \*0.01

#### 13. MEDICAL HISTORY

Medical History conditions are defined as those conditions which stop prior to Screening. Medical History will be collected on the Medical History eCRF and coded using Medical

Dictionary for Regulatory Activities (MedDRA, version 23.0 or higher). Medical History will be summarized for the Safety Set by system organ class (SOC) and preferred term (PT).

#### 14. CONCOMITANT MEDICAL CONDITIONS

Concomitant medical conditions are conditions (other than the indication being studied) which started prior to or at Screening and are ongoing at the date of Screening. Concomitant medical conditions will be captured on the Medical History eCRF page and coded using MedDRA version 23.0 or higher. Concomitant medical conditions will be summarized for the Safety Set by SOC and PT.

#### 15. MEDICATIONS

Medications will be collected on the Prior or Concomitant Medications eCRF and coded using WHODD version 01Mar2020 or higher.

The prior and concomitant medications are defined below. See Appendix 2. Partial Date Conventions for handling of partial dates for medications. In the case where it is not possible to define a medication as prior or concomitant, the medication will be classified by the worst case; i.e., concomitant.

- 'Prior' medications are medications which started and stopped prior to the first dose of study treatment.
- 'Concomitant' medications are medications which started prior to, on or after the first dose of study treatment and continued into the main study period.

Prior and concomitant medications will be summarized separately by ATC Level 3 and Preferred Drug name for the Safety set. In addition, prior and concomitant medications related to IBS will be summarized.

#### 16. STUDY TREATMENT EXPOSURE

The date of first and last study treatment administration will be taken from the eCRF "On Site Dosing Administration" form. Interruptions, compliance, and dose changes are not taken into account for duration of exposure. Study duration and treatment duration will be summarized as continuous variables for each treatment, olorinab 25/50 mg pooled, and pooled olorinab using descriptive statistics. The duration of treatment will also be summarized categorically:  $\leq 4$  weeks,  $\geq 4$  to  $\leq 8$  weeks,  $\geq 8$  weeks. Additionally, the total

subject-years of exposure and subject-years on study will be included in the summary.

Treatment formulation (capsules or tablets), number of capsules/tablets taken, missed, and frequency and percentage of subjects who missed at least one dose or who had at least one dose interruptions recorded on the Dosing Administration eCRF will also be summarized. Treatment compliance will also be summarized using both descriptive statistics and summarized categorically: < 85%,  $\ge 85$  to  $\le 115\%$ , and > 115%.

#### 16.1. DERIVATIONS

- Study Duration (days) = date of last study visit date of screening visit + 1
- Treatment duration (days) = date of last study treatment administration date of first study treatment administration + 1
- Treatment duration (weeks) = (date of last study treatment administration date of first study treatment administration + 1)/7.
- Total subject-years on study = sum of duration of time on study across all subjects divided by 365.25
- Total subject-years of exposure = sum of duration of treatment exposure across all subjects divided by 365.25

#### 17. STUDY TREATMENT COMPLIANCE

Compliance to study treatment will be summarized for the Safety Set. Total number of tablets expected, total number of tablets taken, total number of tablets missed, overall compliance to study treatment, frequency and percentage with overall compliance with the following categories: <85%,  $\ge85\%$  to  $\le115\%$ , and >115%. By-visit compliance will also be summarized.

Subjects with administration compliance greater than 115% and subjects who do not return any study treatment or study packaging will be asked for the reason for the overcompliance or missing study treatment. Their responses will be recorded on the Drug Accountability eCRF and will be listed.

